## Outcome measures

1. Aldehydes are determined using the method described in (Al Rashidi et al., 2008; El-Hellani et al., 2018). In brief, derivatized aldehyde-carbonyl species are extracted from the 2,4-dinitrophenylhydrazine cartridges in 90/10 (vol/vol) ethanol/acetonitrile and quantified by HPLC-UV. We will assess 14 priority aldehyde species that are associated with harm (Table 3).
2. Nicotine in the aerosol and ENDS liquid will be determined by GC-FID as described in (El-Hellani et al., 2015). In brief, nicotine in the aerosol is measured by immersing the filter pads collected in 6 mL water and shaking for 30 minutes. Then, 6 mL toluene is added to extract free-base nicotine. The last step is repeated twice to ensure complete extraction. A solution of NaOH (200 $\mu$ L) is then added to the mixture to convert protonated into free-base nicotine. Nicotine is then extracted using toluene. Total nicotine will be quantified by summing free-base and protonated nicotine.

**Table 3: Aldehydes-carbonyls to be measured at AUB Aerosol Research Lab**

1. Formaldehyde	8. Butyraldehyde
2. Acetaldehyde	9. Benzaldehyde
3. Acetone	10. Valeraldehyde
4. Acrolein	11. Tolualdehyde
5. Propionaldehyde	12. Hexaldehyde
6. Crotonaldehyde	13. Glyoxal
7. Methacrolein	14. Methylglyoxal

## Statistical analysis

Topography data will be processed automatically by the topography instrument software (Spindle et al., 2015, 2017) to eliminate closely spaced puffs (i.e., IPIs < 300 msec). Such puffs are assumed to be part of the previous puff and the recorded volume and duration values will be added to that preceding puff. After this procedure, any puffs less than 5 ml will be considered an artifact and automatically discarded. The remaining data will be averaged for each participant in each condition using all remaining values for puff volume, duration, number, and IPI (Robinson et al., 2018). For plasma nicotine, values below the limit of quantitation (LOQ) will be replaced with the value of the LOQ, 2 ng/mL (Spindle et al., 2017).

Demographic data will be examined and compared to determine if there are significant between-group differences on measures that may be related to study outcome (some differences are expected due to design such as past 30-day ENDS use) though these are expected to be minimized due to randomization. Unexpected between-group differences will be considered as potential adjustment covariates in the primary analysis (Evans et al., 2006). We will generate descriptive statistics which include means, standard deviations, frequencies, and proportions depending on the scale of the outcome by NR factor, time and group assignment. Univariate comparisons of the outcomes by the mentioned conditions will consist of repeated measures ANOVA and paired t-test (for 2X2 within factors) and two-sample t-test for between factor, or their non-parametric equivalents (Wilcoxon signed-rank test and Friedman test for within factors and Wilcoxon Mann-Whitney U test for between factor) if the parametric assumptions are not met. ANOVA will be followed by multiple comparisons with Bonferroni adjustments for multiplicity. Analysis of categorical outcomes will involve a chi-square test of independence for between factors or McNemar's test for paired proportions. The primary analysis of each outcome will involve analysis of variance with two within-subject factors (nicotine concentration: (5%, 3%) or (0% 5%)) and time (pre-post-use). This approach will be extended into a mixed-effects linear regression model to adjust or study the effects of personal attributes such as sex, education, race, and SES. Furthermore, we will consider clinical/physiologic factors such as lung function and respiratory symptoms in a similar modeling approach described above, as a function of experimental factors and demographic covariates, in order to quantify the harm or disease risk. In a case of a non-linear relationship between these factors, we will apply outcome transformations or use non-linear splines to accurately describe these outcomes as a function of

mentioned covariates. Given the known sex-related differences in nicotine dependence (Benowitz et al., 2006), to assess if sex has any effect on the results, it will be considered as a covariate and we will test the pre-planned interaction with it to determine the heterogeneity of the study outcomes by sex as well as potential differential effects. Similarly, for categorical outcomes we will apply generalized linear models and estimating equations with the same main effects as described above, modeling within factors as random effects. We will test for the carry-over effect statistically and will control for it when testing for the primary factors (Senn, 2002).

For Aim 3, we will use a one-way ANOVA to test the effect of NR on aldehyde emissions and multiple linear regression analysis to assess the influence of puff topography data (puff volume, duration, number, and interpuff interval) on aldehyde emissions. Additionally, we will measure the relation between the plasma nicotine levels obtained in the clinical lab and measured nicotine yields obtained in the analytical lab using linear regression. Significance levels will be adjusted for violations of the sphericity assumption using Huynh-Feldt corrections (Keppel, 1991). All differences will be considered significant at the alpha level of 0.05 using adjusted p-values where appropriate. Due to the nature of laboratory data collection, missing data is rare and it usually occurs due to instrument malfunction. All data are collected and checked for completeness by laboratory staff. In the case of missing data, which we expect to be minimal, we will use a regression model based on multiple imputations with all available outcome data, demographic, and clinical variables as predictors. This will be carried out in 25 random repetitions under missing at random assumption, analyzed using methods described above and results will be combined to produce unbiased overall estimates and standard errors of the experimental conditions. As a sensitivity analysis completers results will be compared with multiple imputation results.

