Screening, and informed consent: Individuals who are identified as potentially eligible based on the phone screening will be asked to attend an onsite-screening, which will involve assessment of inclusion/exclusion criteria, physical examination, COVID-19 screening, and urine pregnancy testing for women. Prior to screening, potential participants will undergo a review of the study and consent procedures to ensure that they understand the study, its risks/benefits, and their rights as research participants. Consented (written) individuals will then undergo a physical examination conducted by the research nurse, who will have access to an on-call Medical Monitor (physician) in case of concern or for consultation at any point of the study as it is the standard practice in our lab. Successfully consented participants will be scheduled for their 1st session and asked to abstain from all tobacco/nicotine use 12 hours prior to it.

Sample size. All power calculations were performed with PASS19 (PASS, 2019). We built our calculation of the sample size for this study based on our preliminary study of the effect of NR on subjective (e.g. craving, urges) and puff topography measures (pls. see Preliminary Studies), where medium effect size (Cohen's  $f=0.2$ ) depending on nicotine condition was detected. Expecting a maximum 20% loss due to noncompliance with abstinence or study protocol (Vargas-Rivera et al., 2020), this study will include a dropout inflated sample of 150 ENDS users. Using repeated measures ANOVA F-test with 2 within and 1 between factors, a total dropout adjusted sample size of 120 (2X60) participants will have at least 80% power to detect small to medium-size effect (Cohen's  $f=0.1-0.2$ ) or larger for 2 within-subject (NR condition and time) and 1 between subject (use frequency) factors, as well as their interactions at 0.05 level of significance, assuming sphericity and a moderate correlation (0.5) among repeated measures (Cohen, 1988).

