Experimental protocol. Participants from each frequency group will be randomly assigned to one of the nicotine concentration conditions and attend the lab for two, ~2-h sessions, separated by a 48-h washout period, and differ by nicotine concentration (3%,5%) or (0%, 5%). Session order will be counterbalanced to mitigate order and carry-over effects. At the beginning of the 1st session, participants will provide consent, complete demographic and personal information including age, sex, socioeconomic status, race/ethnicity, and detailed tobacco/nicotine use history. Participants will get familiarized with the study procedures, measures, and they will be given time to adapt to the lab. After adaptation, continuous measurement of physiological responses begins, and 10 ml of venous blood is sampled, lung function tests will be conducted, and participants are asked to respond to subjective measures (pls. see below Outcome Measures). Participants will inhale on their session ENDS ad libitum for up to 60 minutes (as in Vargas-Rivera et al., 2020). At the end of the ENDS use period 10 ml of blood will be sampled, lung function tests repeated, and subjective measures assessed. The session will terminate 30 minutes after the last puff, and the 2nd session is scheduled. A follow-up phone call at 3-month post-study will be made to evaluate nicotine preferences and changes in ENDS and tobacco use.

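### The stated primary ANOVA has no use-frequency term, although the study is powered on that factor and its interactions and two aims depend on it

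*Combined protocol and SAP*

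**What the plan says.** The Statistical analysis section gives the primary model: "The primary analysis of each outcome will involve analysis of variance with two within-subject factors". The two factors are nicotine concentration and time. No between-subject term is named. A between factor appears only among the univariate comparisons, where it is tested by a two-sample t-test or its rank equivalent.

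The sample size paragraph, under Participants and recruitment, describes a different model: "Using repeated measures ANOVA F-test with 2 within and 1 between factors". It identifies the between factor as "1 between subject (use frequency) factors, as well as their interactions".

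The experimental protocol paragraph makes frequency the frame for assignment: "Participants from each frequency group will be randomly assigned to one of the nicotine concentration conditions".

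On covariates, the Statistical analysis section begins with baseline testing: "Demographic data will be examined and compared to determine if there are significant between-group differences". It allows that "some differences are expected due to design such as past 30-day ENDS use", and adds "though these are expected to be minimized due to randomization". The rule then follows: "Unexpected between-group differences will be considered as potential adjustment covariates in the primary analysis". Separately, an extension to a mixed-effects model names sex, education, race and SES. Sex also has a pre-planned interaction, and carry-over is to be tested and controlled for.

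**The concern.** Aim 1 predicts that the effect of nicotine reduction on satisfaction, withdrawal and intention to use will be larger in high- than in low-frequency users. Aim 2 predicts the same for compensatory puffing. The third regulatory question in the Background asks about users at different stages of use. All three are questions about a frequency-by-nicotine interaction, and a model containing only nicotine and time has no coefficient for one. The analyst would have to add it after the fact, choosing how to form the groups, which interactions to fit and which covariates to include, or else fall back on the univariate t-test.

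The covariate rule adds a smaller problem. The example of a by-design difference is past 30-day use, which suggests that the frequency groups are among those being compared. Frequency is a characteristic that participants bring with them, so randomisation gives no reason to expect high and low users to be alike on age, other tobacco use or dependence. A significance test in groups of this size is a weak way to find the differences that matter.

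**Working it through.** **1. The plan's own figure.** Enrolment: 120/(1 − 0.20) = 150, as stated. For power, the inputs from the sample size paragraph are N = 120, correlation ρ = 0.5, alpha 0.05 and f = 0.1 to 0.2. I take m = 4 repeated cells (2 nicotine × 2 time) and, as an assumption, two frequency groups, so F has 1 and 118 df.

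- Within-subject and interaction terms: λ = f²Nm/(1 − ρ). At f = 0.1, 0.01 × 120 × 4/0.5 = 9.6, power 86.7%.
- Between-subject term: λ = f²Nm/(1 + (m − 1)ρ). At f = 0.2, 0.04 × 120 × 4/2.5 = 7.68, power 78.5%. At f = 0.1, λ = 1.92, power 28%.

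The claim of at least 80% is thus reproduced, to within 2 points, if f = 0.1 refers to the within and interaction terms and f = 0.2 to frequency. The calculation needs frequency in the model.

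**2. Model against hypotheses.**

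| Source | Frequency term |
|---|---|
| Sample size | main effect and interactions |
| Experimental protocol | assignment made from each frequency group |
| Aims 1 and 2, regulatory question 3 | effect of nicotine reduction by frequency or stage of use |
| Primary ANOVA | none |
| Univariate comparisons | two-sample t-test for an unnamed between factor |

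A two-sample t-test on an outcome compares levels. It would test the interaction only if applied to each person's difference between nicotine conditions, and the plan does not say that.

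**3. Effect on the nicotine contrast.** Adding a frequency main effect does not move it. In a simulated balanced data set the estimate was 0.183 and its standard error 0.125 with no covariate, with frequency, and with frequency plus a covariate. Leaving out the interaction costs power only if response really differs by frequency. With 60 people and nominal power of 80%, power for the average contrast is about 78%, 73% and 65% when the groups' contrasts differ by 0.5, 1.0 and 1.5 SD of the paired difference. With the term included it stays at about 80 to 81%.

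**4. The test-then-adjust rule.** Assumed, since the plan gives no figures: one covariate differing by 0.3 SD between equal frequency groups, correlated 0.5 with outcome, no true group effect. The groups are 30 v 30 within one part, or 60 v 60 pooled.

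- Chance of a flag at p < 0.05: noncentrality 0.3 × √(n/2). For n = 30 this is 1.16 (58 df), giving 21%. For n = 60 it is 1.64 (118 df), giving 37%.
- Mean bias in the high v low difference in level under the rule (20,000 simulated studies): about 0.08 SD at 30 v 30 and 0.06 SD at 60 v 60. Type I error is about 0.05 to 0.06.
- Bias in frequency-by-nicotine: the covariate adds the same amount under both nicotine conditions, so it cancels within person. The simulated value is about 0.00 SD at both sizes.

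For scale, f = 0.1 to 0.2 corresponds to 0.2 to 0.4 SD between two equal groups (d = 2f).

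**The case against.** The best defence is that the covariate rule does little harm. The frequency hypotheses are interactions, a covariate that shifts level cancels from them, and type I error hardly moves. That stands. It also means that adding main-effect covariates would not by itself protect the contrast the aims care about.

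Three stronger readings are tempting, and the documents do not support them.

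- A reader might infer that covariates can enter the analysis solely through a significant baseline difference. Sex, education, race and SES are named for the extension model whatever the imbalance, and sex has its own planned interaction. The screening rule says only that variables will be considered. What remains is that this rule is the one tied by name to the primary analysis, and that the extension list is illustrative and does not name frequency.
- A reader might infer that the plan presents the high v low comparison as protected by randomisation. It does not say so. It never defines which groups are compared, and the remark is correct for the randomised condition pairs.
- A reader might put the bias at 0.3 × 0.5 = 0.15 SD. That is the bias of never adjusting. Under the stated rule flagged studies are adjusted, and unflagged ones tend to have smaller observed imbalance.

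Eligibility also narrows two obvious confounders: age is limited to 21 to 35, and other tobacco use to at most 5 times in the past month.

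None of this supplies the missing frequency term.

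**Conclusion.** The point holds as an inconsistency between the primary model and the rest of the plan. The study is powered on use frequency, assigns participants from frequency groups and hypothesises about frequency, but the stated primary ANOVA cannot test those hypotheses. This rests on the text alone.

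The covariate rule is a secondary weakness. The sizes in step 4 depend on the assumed 0.3 SD imbalance, the 0.5 correlation and equal groups, because the plan gives no split by frequency. The interaction would be biased only if the covariate changes the response to nicotine, and the documents give no figure for that. The average within-person nicotine contrast is not biased by the omission in complete, balanced data. This is a minor matter of specification and no reason to doubt the design.

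**What to change.** - Put use frequency in the primary model with its interaction with nicotine concentration and, for outcomes measured before and after use, its interactions with time and with nicotine by time. Include session order.
- Name the frequency-by-nicotine term as the test of the frequency hypotheses in Aims 1 and 2.
- Define the frequency groups, and say which groups the baseline comparison refers to.
- Replace the test-then-adjust rule with a short fixed list of covariates already collected, for example age, sex and other tobacco use. Where the frequency-by-nicotine claim is to be adjusted, add covariate-by-nicotine terms.
- Describe the high v low contrast as observational.

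The cost is a few sentences and a few degrees of freedom. With two frequency groups, the frequency term takes the error df from 59 to 58 in a part of 60, and session order and each covariate take a little more. The sample size stays at 120 evaluable and 150 enrolled, because the power calculation already counts this factor. That calculation is for all 120. If the ANOVA is run within each part of 60, power is about 58% for a within or interaction effect of f = 0.1 and about 49% for a frequency effect of f = 0.2, so the plan should also say whether the parts are pooled for the frequency terms and, if so, include condition pair.

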## **Study Design**

This study is divided into 2 parts (studies), whereby the first part will be 2X2 comparing NJOY 5% and 3% to test the effects of partial nicotine reduction, and the second part will be using the NIDA Standardized Research Electronic Cigarette (SREC) for Clinical Research 5% and 0% (placebo), to test the effect of the total reduction using the same pods and juices from the same manufacturer.

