Recruitment: We will recruit participants using a combination of online, offline, and in-person recruitment methods to ensure successful recruitment (Buller et al., 2012). Offline items such as posters, flyers, and study inserts will be posted and distributed on FIU and other university campuses in Miami (e.g. University of Miami), nearby off-campus locations, and around ENDS shops in Miami. Online recruitment will include student listservs, Facebook, and other social media. In-person recruitment will involve handing out flyers and word-of-mouth targeting vape shops in Miami. Recruitment materials will be Institutional Review Board (IRB) approved and will have contact information (phone, e-mail) for initial eligibility screening. Based on previous experience, we expect to study 10 subjects/month (Vargas-Rivera et al., 2020). We will continue recruitment until we reach the target sample (120 with complete sessions). While recruitment is

always a challenge, [name]'s lab has easily recruited JUUL users in the past year with negligible drop out for 2 session protocol using comparable incentives, to the extent that we had to turn down many eligible participants due to sampling saturation (Vargas- Rivera et al., 2020). This is due to the widespread use of ENDS, and JUUL among young adults, especially in a large university with about 57,000 students such as FIU, where our lab is located. Participants completing the on-site screening and 2 lab sessions, and 3-month phone follow-up will be compensated a total \$200 at the end of the study to encourage completeness.

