## **AIM 3: To assess exposure to toxicants associated with nicotine reduction.**

**Objective and hypothesis:** This aim will help elucidate how compensatory puffing behavior in response to NR affects exposure to pulmonary toxicants. *We hypothesize that partial but not total NR will be associated with compensatory puffing behavior that will, in turn, lead to greater exposure to toxicants.*

**Analytical methods.** The analytical assessments will be conducted at the AUB Aerosol Research Laboratory (ARL). The ARL is equipped with two digital playback smoking machines necessary for Aim 3. These two machines, developed and tested by our team at AUB, are to our knowledge unique to this setting and are not available in any other laboratory. The proposed work in Aim 3 is built on the ARL framework and infrastructure for aerosol generation, sampling, and chemical analysis.

**Aerosol generation and sampling:** The deidentified puff topography data will be shared via Microsoft Sharepoint between FIU and AUB Aerosol Lab, thus, all communication will be encrypted between client and server using SSL 2048 bit keys. Access to the lab and data will be granted only by permission of Drs. [name] (PI), and [name] (local PI at AUB).

Once the puff topography files have been received by the ARL, we will use ALVIN (Aerosol Lab Vaping Instrument) (Talih et al., 2015, 2017) to draw aerosols from the ENDS devices, for each of the 240 topography sessions. For each session, ALVIN will be programmed to reproduce the puff topography data generated in the clinical lab. The generated aerosol will be drawn through a Gelman type A/E 47mm glass fiber filter followed by a 2,4-dinitrophenylhydrazine-coated silica cartridge (type LpDNPH H10) cartridge, for nicotine and aldehydes quantification, respectively (see Talih et al., 2015, 2017; El-Hellani et al., 2018 for more detail). The pods (e.g. JUUL) and batteries will be shipped from the same batch as those used at FIU to minimize biases. A new pod will be used for every session. Each pod will be pre-conditioned before sampling by drawing 15 4-second puffs at 1 LPM using ALVIN. We will use a quality assurance protocol and ENDS electrical performance tester developed at the ARL to ensure that each battery and pod are within tolerance (Talih et al., 2019, 2020b).

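### The primary analysis leaves out use frequency and its interaction with nicotine condition, so Aim 2's only hypothesis and the high-versus-low part of Aim 1 have no specified test

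*Combined protocol and SAP*

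**What the plan says.** **Power model.** The Sample size paragraph (under Participants and recruitment) describes a repeated measures ANOVA with two within factors and one between factor. It claims that "a total dropout adjusted sample size of 120 (2X60) participants will have at least 80% power" at Cohen's f of 0.1 to 0.2, "for 2 within-subject (NR condition and time) and 1 between subject (use frequency) factors, as well as their interactions", with alpha 0.05 and a correlation of 0.5.

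**Allocation.** The Experimental protocol paragraph says: "Participants from each frequency group will be randomly assigned to one of the nicotine concentration conditions".

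**Hypotheses.** AIM 2 has one hypothesis: compensatory puffing under NR is stronger in high- than in low-frequency users. AIM 1 predicts, among other things, that NR effects are larger in high-frequency users. The third regulatory question in the Background asks about users at different stages of use.

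**Analysis.** The Statistical analysis section says: "The primary analysis of each outcome will involve analysis of variance with two within-subject factors", and names these as concentration and pre-post time. The mixed-model extension covers "effects of personal attributes such as sex, education, race, and SES". Models for categorical outcomes carry the same main effects. The one interaction called pre-planned is with sex.

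**Outcome timing.** Table 2 places puff topography in the During column only, and the Statistical analysis section averages it to one value per participant per condition.

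**The concern.** A hypothesis that NR acts more strongly in one group than in another is a hypothesis about an interaction. A model with condition and time only estimates the NR effect averaged over frequency groups. It gives the same expected answer whether compensation is confined to high-frequency users or equal in everyone. An analyst could follow the Statistical analysis section to the letter and never test the one hypothesis that Aim 2 states.

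The two descriptions of the model also disagree. The power paragraph and the allocation treat frequency as a design factor; the primary analysis does not. For topography, the outcome on which Aim 2 turns, the stated two-factor ANOVA cannot be fitted at all, because there is no pre-use value.

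**Working it through.** **Inputs.** From the Sample size paragraph: N = 120, loss 20%, f = 0.1 to 0.2, rho = 0.5, alpha = 0.05. From the design: m = 4 measurements per person for pre-post outcomes (2 conditions x 2 times), m = 2 for once-per-session outcomes. Assumed, because the documents do not say: two frequency groups of equal size, and an equal split of the 120 over the two study parts (60 each). That 120 is the total over both parts follows from Aim 3: 120 x 2 sessions = 240, matching playback "for each of the 240 topography sessions".

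**Step 1: reproduce the plan's figures.** Enrolment: 120 / (1 - 0.20) = 150, as stated. Power uses the noncentral F with 1 and N - 2 degrees of freedom.
- Within effects and their interactions with frequency: lambda = f² x N x m / (1 - rho). At f = 0.1, N = 120, m = 4: 0.01 x 120 x 4 / 0.5 = 9.6, power 87%.
- Frequency main effect: lambda = f² x N x m / (1 + (m - 1) x rho). At f = 0.2: 0.04 x 120 x 4 / 2.5 = 7.68, power 78.5%.
- Smallest f with 80% power: 0.091 for within effects and interactions, 0.204 for frequency. This matches the stated range of 0.1 to 0.2.

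So the power paragraph reproduces as a three-factor model with use frequency in it.

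**Step 2: what the stated primary test can see.** Take a once-per-session outcome with unit SD. The within-person NR difference has SD sqrt(2 x (1 - 0.5)) = 1. At f = 0.2 the difference in NR effect between frequency groups is 4f = 0.8 SD. Two scenarios have the same average effect of 0.40 SD. The condition test is a paired t; the interaction test is a two-sample t on within-person differences. Simulated rejection rates:

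| Scenario (high, low) | N | Condition test (in plan) | Condition x frequency (not in plan) |
|---|---|---|---|
| A: 0.8, 0 | 60 | 82% | 86% |
| B: 0.4, 0.4 | 60 | 86% | 5% |
| A: 0.8, 0 | 120 | 99% | 99% |
| B: 0.4, 0.4 | 120 | 99% | 5% |

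The frequency hypothesis is true in A and false in B. The stated test does not separate them.

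**Step 3: power of the missing term.** Same formula as for within effects, lambda in brackets:

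| Outcome and test | N | f = 0.1 | f = 0.2 |
|---|---|---|---|
| Pre-post, condition x time x frequency (m = 4) | 120 | 87% (9.6) | above 99% (38.4) |
| Pre-post, same test, one part | 60 | 58% (4.8) | 99% (19.2) |
| Once per session, condition x frequency (m = 2) | 120 | 58% (4.8) | 99% (19.2) |
| Once per session, same test, one part | 60 | 33% (2.4) | 86% (9.6) |

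The claim of at least 80% holds at f = 0.1 for pre-post outcomes with all 120 analysed together. It does not hold at f = 0.1 for topography, or for a single part.

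**The case against.** The best defence is that frequency is present in the plan, only not in the primary-model sentence.

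- **The power paragraph names the model.** It does, and it shows the intention. But it is a sample-size statement, and the section that governs the analysis says something different.
- **Descriptives are planned by group assignment, and past 30-day use is listed as a difference expected by design.** If those groups are the frequency groups, means by condition, time and frequency would be tabulated. It would then be wrong to infer that nothing on frequency would be reported. What is missing is an inferential test.
- **A two-sample t-test is planned for the between factor.** It would equal the interaction test only if applied to within-person NR differences, and the plan does not say so. Comparing outcome levels between high- and low-frequency users does not show whether their response to NR differs.
- **The covariate list is open-ended.** Adding frequency as a covariate still would not specify its interaction with NR.
- **The simulation is built so that the averages agree.** That is so. It illustrates which question each test answers and does not measure a loss in this trial.

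A reader might also infer that the high/low split will be picked after the data are seen. The documents do not support that: assignment is made from within frequency groups, so the groups exist at allocation. The cut-off is unwritten, which is a smaller fault. Nor was the sample size derived from the interaction: the effect size came from a preliminary NR-condition effect, and the interactions enter only through the power claim.

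**Conclusion.** The point holds and should be fixed before analysis. The primary analysis contradicts the power paragraph and the stratified assignment, and it leaves Aim 2's sole hypothesis and the high-versus-low part of Aim 1 without a specified test. Separately, its pre-post factor cannot be applied to puff topography.

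A reader might go further and conclude that the power statement is false. It is not: with four measurements and N = 120 the interaction has 87% power at f = 0.1. The statement is incomplete, because it does not say which test, outcome type and N it covers. At f = 0.1, power is 58% (N = 120) or 33% (N = 60) for once-per-session outcomes, and 58% for pre-post outcomes in one part. At f = 0.2 it is at least 86% in all these cases.

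The figures rest on rho = 0.5 and alpha 0.05 (the plan's values), on equal frequency groups (assumed) and, for N = 60, on an equal split between the parts (assumed). The omission itself rests on the text alone.

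**What to change.** In **Statistical analysis**, rewrite the primary-model sentence:

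1. Add use-frequency group and its interactions. Use the grouping applied at allocation, and write down its cut-off.
2. For outcomes with pre and post values, test the frequency hypothesis by condition x time x frequency.
3. For once-per-session outcomes such as topography, drop time and test condition x frequency.
4. Report the NR x frequency estimate for each study part, since the parts use different products. If the parts are combined, include study part and its interaction with condition. This also serves Aim 1's comparison of total with partial NR, which separate analyses of the two parts would leave untested.
5. If the two-sample t-test is meant to address these hypotheses, say that it is applied to within-person NR differences.

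In **Sample size**, say what 2X60 refers to, and which test and N the power claim covers.

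The cost is wording and one between-subject error degree of freedom per part (59 to 58 with 60 participants). No new data are needed: frequency of use is already a baseline measure and already part of the assignment.
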